5.2 Exclusion Criteria

An individual who meets any of the following criteria will be excluded from participation in this study:

1. Currently pregnant
2. Currently breastfeeding
3. Have taken oral retinoids within 6 months of study initiation
4. Has had keloid treatment within 1 month of study initiation
5. Has active infection at treatment site
6. Has active malignancy
7. Presence of pedunculated keloid(s) or keloid(s) that are judged to be best treated with surgical excision first
8. Hypertrophic scars
9. Known hypersensitivity to TAC or 5-FU
10. Chronic systemic corticosteroid or immunosuppressive medication use
11. Has intolerance to anesthesia
12. Has known connective tissue disease
13. Has known infectious disease

5.4 Duration of Study Participation

Duration of study participation will be 1 year.

5.5 Total Number of Participants and Sites

Recruitment will end when approximately 30 participants are enrolled. It is expected that approximately 30 participants will be enrolled in order to produce 20 evaluable participants (projected accrual is 20).

The site of this study will be at [name]. Treatments will take place on the 24th floor.

CONFIDENTIAL

This material is the property of the NYU School of Medicine and Langone Medical Center. Do not disclose or use except as authorized in writing by the study sponsor
Interventional Template Version: 11 January 2019

5.6 Participant Withdrawal or Termination

5.6.1 Reasons for Withdrawal or Termination

Participants are free to withdraw from participation in the study at any time upon request. An investigator may terminate participation in the study if:

- Any clinical adverse event (AE), laboratory abnormality, or other medical condition or situation occurs such that continued participation in the study would not be in the best interest of the participant
- The participant meets an exclusion criterion (either newly developed or not previously recognized) that precludes further study participation

Participants will be terminated from the study if there is no clinical response noted by Visit #3.

5.6.2 Handling of Participant Withdrawals or Termination

If a participant withdraws from the study, the investigator(s) will ask if the information already collected can still be used as part of the study.

5.7 Premature Termination or Suspension of Study

This study may be temporarily suspended or prematurely terminated if there is sufficient reasonable cause. Written notification, documenting the reason for study suspension or termination, will be provided by the suspending or terminating party to the primary investigator. If the study is prematurely terminated or suspended, the PI will promptly inform the IRB and will provide the reason(s) for the termination or suspension.

Circumstances that may warrant termination or suspension include, but are not limited to:

- Determination of unexpected, significant, or unacceptable risk to participants

Study may resume once concerns about safety, protocol compliance, and data quality are addressed and satisfy the IRB and/or FDA.

6 Study Agent (Study drug, device, biologic, vaccine etc.) and/or Procedural Intervention

6.1 Study Agent(s) and Control Description

5-FU is a chemotherapeutic drug. This medication is kept routinely in the dermatology clinic for intradermal injection. The needles and syringes involved will be disposed of in the labeled clinic sharps container.

For TAC solution, the needles and syringes involved will be disposed of in the labelled clinic sharps container.

6.1.1 Acquisition

Both 5-FU and TAC are routinely available at the NYU Dermatology Faculty Group Practice. These medications are ordered from the Henry Schein medical supplier.

6.1.2 Formulation, Appearance, Packaging, and Labeling

5-FU is a opaque white liquid that comes in a clear glass bottle. This medication comes in the dose 50mg/mL.

TAC solution is a clear colorless solution that comes in a clear glass bottle in the dose 10mg/mL. We will use this medication at the dose 10mg/mL.

CONFIDENTIAL

This material is the property of the NYU School of Medicine and Langone Medical Center. Do not disclose or use except as authorized in writing by the study sponsor
Interventional Template Version: 11 January 2019

6.1.3 Product Storage and Stability

Both 5-FU and TAC are stable at room temperature.

6.1.4 Preparation

Neither 5-FU or TAC will need to be reconstituted; as such, both medications will be drawn up as is.

6.1.5 Dosing and Administration

5-FU will be used at the dose of 50 mg/mL and TAC will be used at the dose of 10mg/mL.

6.1.6 Route of Administration

Planned route of administration is laser-assisted delivery topically

6.1.7 Dose Adjustments/Modifications/Delays

Dose adjustments will be not be made to TAC or 5-FU. Adjustments will be made to the laser settings (density, depth) depending on the thickness of the keloid at the time of treatment.

6.1.8 Duration of Therapy

Therapy duration is 4 total treatments spaced 4 weeks \pm 1 week apart.

6.1.9 Tracking of Dose

Dose will be fixed at 50 mg/mL for 5-FU and 10 mg/mL for TAC.

6.1.10 Device Specific Considerations

The laser utilized in our study is the Sciton Joule. Settings depend on the keloid thickness and will range from 400micron – 1mm in depth, 5.5-11% density, single pass, without coagulation. Contraindications to using this device are as follows:

- Patients intolerant of anesthesia
- Patients with infectious disease
- Patients with connective tissue disease
- Patients with history of immunocompromise
- Patients who are pregnant
- Patients who have used isotretinoin within the past year
- Patients with a medical condition that may affect wound healing
- Patients who use anticoagulant medications

6.2 Study Procedural Intervention(s) Description

The procedural intervention in this study is laser-assisted drug delivery with use of fractional ablative erbium laser.

- Randomization of either which side of lesion (Right or Left) or which lesion (if two comparable lesions present) will be treated with laser-assisted TAC v laser-assisted 5-FU.
- Subjects Passing Screening will immediately have visit one as outlined in Visits 1-4

7.2.1 Treatment Visits

Visits 1 - 4

- Urine pregnancy test if female of child-bearing age. (visits 2-4)
- Physical examination of lesion of interest.
- Photography of lesion (keloid) of interest, taken before any treatment is performed
- Measurement (height, length, width) of lesion (keloid) of interest performed at the start of the visit, before treatment
- Completion of POSAS (including monitoring of adverse events) by patient and providers at the start of the visit
- Administer the study treatment (to be performed by PI): laser assisted drug-delivery treatment of both 5-FU and TAC.
- Monitoring of adverse events
- Patients will be asked about side effects (non-serious adverse events) from laser treatment on visits 2-4
- Patients will be asked to grade their post-procedure pain on a scale of 1 to 10 on visits 2-4
- Patients will be asked which side healed faster after the laser treatment on visits 2-4
- Post-treatment instructions will be provided to patients on an after-treatment instruction sheet: gentle cleansing of area with soap and water twice a day, apply petrolatum jelly and keep area covered for 1 week, avoid sun exposure to treated area(s) for study duration.
- Visits will take place every 4 weeks ± 1 week.

7.2.2 Final Study Visit

Visit 5

- Photography of lesion (keloid) of interest to be reviewed by blinded physician observers
- Measurement (height, length, width) of lesion (keloid) of interest
- Completion of POSAS (including monitoring of adverse events)
- Patients will be asked about side effects (non-serious adverse events) from laser treatment
- Patients will be asked to grade their post-procedure pain on a scale of 1 to 10
- Patients will be asked which side healed faster after the laser treatment

7.2.3 Withdrawal/Early Termination Visit

Photography and lesion measurements (length, width, height) should be done at a termination visit if a subject withdraws or if early termination occurs, provided the participant is willing.

7.2.4 Unscheduled Visit

Unscheduled visits pertaining to the lesion of interest will be documented as an extra visit.

CONFIDENTIAL

This material is the property of the NYU School of Medicine and Langone Medical Center. Do not disclose or use except as authorized in writing by the study sponsor
Interventional Template Version: 11 January 2019

7.3 Prophylactic Medications, Treatments, and Procedures

Intralesional 1% lidocaine with epinephrine 1:100,000 will be used for anesthesia prior to each laser-assisted drug delivery treatment session.

8 Assessment of Safety

8.1.1 Definition of Adverse Events (AE)

An **adverse event** (AE) is any symptom, sign, illness or experience that develops or worsens in severity during the course of the study. Intercurrent illnesses or injuries should be regarded as adverse events. Abnormal results of diagnostic procedures are considered to be adverse events if the abnormality:

- results in study withdrawal
- is associated with a serious adverse event
- is associated with clinical signs or symptoms
- leads to additional treatment or to further diagnostic tests
- is considered by the investigator to be of clinical significance

8.1.2 Definition of Serious Adverse Events (SAE)

Serious Adverse Event

Adverse events are classified as serious or non-serious. A **serious adverse event** is any AE that is:

- fatal
- life-threatening
- requires or prolongs hospital stay
- results in persistent or significant disability or incapacity
- a congenital anomaly or birth defect
- an important medical event

Important medical events are those that may not be immediately life threatening, but are clearly of major clinical significance. They may jeopardize the subject, and may require intervention to prevent one of the other serious outcomes noted above. For example, drug overdose or abuse, a seizure that did not result in in-patient hospitalization, or intensive treatment of bronchospasm in an emergency department would typically be considered serious.

All adverse events that do not meet any of the criteria for serious should be regarded as **non-serious adverse events**.

8.1.3 Definition of Unanticipated Problems (UP)

Unanticipated Problems Involving Risk to Subjects or Others

Any incident, experience, or outcome that meets all of the following criteria:

- Unexpected in nature, severity, or frequency (i.e. not described in study-related documents such as the IRB-approved protocol or consent form, the investigators brochure, etc)
- Related or possibly related to participation in the research (i.e. possibly related means there is a reasonable possibility that the incident experience, or outcome may have been caused by the procedures involved in the research)
- Suggests that the research places subjects or others at greater risk of harm (including physical, psychological, economic, or social harm).

This definition could include an unanticipated adverse device effect, any serious adverse effect on health or safety or any life-threatening problem or death caused by, or associated with, a device, if that effect, problem, or death was not previously identified in nature, severity, or degree of incidence in the investigational plan or application (including a supplementary plan or application), or any other

CONFIDENTIAL

This material is the property of the NYU School of Medicine and Langone Medical Center. Do not disclose or use except as authorized in writing by the study sponsor
Interventional Template Version: 11 January 2019

unanticipated serious problem associated with a device that relates to the rights, safety, or welfare of subjects (21 CFR 812.3(s)).

8.2 Classification of an Adverse Event

8.2.1 Severity of Event

For AEs not included in the protocol defined grading system, the following guidelines will be used to describe severity.

- **Mild** – Events require minimal or no treatment and do not interfere with the participant's daily activities.
- **Moderate** – Events result in a low level of inconvenience or concern with the therapeutic measures. Moderate events may cause some interference with functioning.
- **Severe** – Events interrupt a participant's usual daily activity and may require systemic drug therapy or other treatment. Severe events are usually potentially life-threatening or incapacitating.

8.2.2 Relationship to Study Agent

The clinician's assessment of an AE's relationship to study agent (drug, biologic, device) is part of the documentation process, but it is not a factor in determining what is or is not reported in the study. If there is any doubt as to whether a clinical observation is an AE, the event should be reported. All AEs must have their relationship to study agent assessed. In a clinical trial, the study product must always be suspect. To help assess, the following guidelines are used.

- **Related** – *The AE is known to occur with the study agent, there is a reasonable possibility that the study agent caused the AE, or there is a temporal relationship between the study agent and event. Reasonable possibility means that there is evidence to suggest a causal relationship between the study agent and the AE.*
- **Not Related** – *There is not a reasonable possibility that the administration of the study agent caused the event, there is no temporal relationship between the study agent and event onset, or an alternate etiology has been established.*

8.2.3 Expectedness

[name] (PI) will be responsible for determining whether an AE is expected or unexpected. An AE will be considered unexpected if the nature, severity, or frequency of the event is not consistent with the risk information previously described for the study agent.

10.1 Sample Size Considerations

We will recruit and screen 30-40 participants with a projected accrual of 20 evaluable patients.

A sample size of 20 patients with a significance level (alpha) of 0.05 using a two-sided paired Wilcoxon Signed-Rank test (assuming that the actual distribution of paired differences is normal) can achieve 80% power to detect the following means of the paired difference between both Sites in the change from the first POSAS score (before initiating treatment series) to the final POSAS score.

We present in the table below a number of detectable means based on various estimated standard deviations (SD) of the paired differences between both treatments in the change from the first POSAS score to the final POSAS score. The estimated SD's are based on various assumptions of Pearson's correlation coefficients between the first POSAS score and the final POSAS score and between both treatments of the keloid (we assumed that the correlation between the first POSAS score and the final POSAS score is similar to the correlation between both treatments). Additionally, for an estimation of

CONFIDENTIAL

This material is the property of the NYU School of Medicine and Langone Medical Center. Do not disclose or use except as authorized in writing by the study sponsor
Interventional Template Version: 11 January 2019

standard deviation of the POSAS score, we used the difference in its range divided by 4, i.e. $(120-12)/4=27$.

:

Correlation coefficient between the first POSAS score (before initiating treatment series) and the final POSAS score and between both treatments	Estimated SD of the paired difference between both treatments in the change from the first POSAS score (before initiating treatment series) to the final POSAS score	Detectable mean of paired difference between both treatments in the change from the first POSAS score (before initiating treatment series) to the final POSAS score
0.1	48.6	33.0
0.25	40.5	27.5
0.5	27.0	18.4
0.75	13.5	9.2
0.9	5.4	3.7

10.2 Statistical Methods

10.2.1 General Methods

Continuous variables will be summarized using descriptive statistics (n, mean, standard deviation, median, minimum, and maximum). Categorical variables will be summarized showing the number and percentage (n, %) of patients within each classification. Graphical displays will be provided where useful in the interpretation of results.

10.2.2 Demographics and Baseline Characteristics

Demographic data (gender, age [years], age group, race, ethnicity), baseline scar characteristics and POSAS scores at baseline will be summarized.

10.2.3 Primary Analysis

Prior to the analysis, distributions of the POSAS scores will be summarized by visit and the distributions of the modified Hamilton scores will be summarized at the final visit.

A two-sided paired Wilcoxon Signed-Rank test at a 0.05 significance level will be used to compare Site A and Site B of the keloid in the change from the first POSAS score (before initiating treatment series) to the final POSAS score.

A two-sided paired Wilcoxon Signed-Rank test at a 0.05 significance level will be used to compare the modified Hamilton score in Site A and Site B of the keloid.

10.2.4 Secondary Analysis

The measurements of the scar will be defined as the total volume (length x width x height) in cm^3 of the scar, or length x width in cm^2 if the scars are flush with the surrounding skin scar surface.

Measurements of the scar will be summarized by visit and compared between the two Sites of the keloid.

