Endpoints	
Primary Endpoint 1. The first primary endpoint is the POSAS score in Site A and Site B at first visit (pre-treatment) and last visit (post-treatment). 2. The second primary endpoint is a modified Hamilton score based on comparing clinical photographs of the scarred skin and healthy skin next to each other in Site A and Site B.
 
Secondary Study Endpoints The secondary endpoint is measurements of the scar in both Sites of the keloid. The measurements will be calculated as the total volume (length x width x height) in cm³ of the scar, or length x width in cm² if the scars are flush with the surrounding skin. Scar surface will be measured in both Sites of the keloid treated with laser-assisted 5-FU delivery as compared to laser-assisted TAC.
 
Exploratory Endpoints Patient's subjective experiences measured as follows:
 
1. Patient perceived side effects after each treatment at visits 1, 2, 3, and 4 in Site A and Site B, in terms of dyspigmentation, pain, itch, swelling.2. Pain grade after each laser treatment at visits 1, 2, 3, and 4, measured on a scale of 1 to 10 (10 being the worst pain), in Site A and Site B, recorded at the subsequent follow up visit.3. Perceived speed of healing at final visit (visit 5) will be compared between both Sites using the following answers: Site A healed faster than Site B, Site B healed faster than Site A, Same speed of healing in both Sites
Study Duration	2 years
Participant Duration	1 year
Duration of IP administration	Up to 6 months
Population	Healthy men and women ages 18-89 in the United States.
Study Sites	NYU Dermatologic Surgery Associates.
Number of participants	20 participants.
Description of Study Agent/Procedure	The intervention will be a split-scar fractional ablative erbium laser-assisted delivery of 50mg/mL of 5-fluorouracil solution to one half of the scar and 10 mg/mL of triamcinolone acetonide solution to the other half of the scar. Patients will undergo 4 treatments.
Reference Therapy	N/A
Key Procedures	Laser therapy as above.

CONFIDENTIAL

This material is the property of the NYU School of Medicine and Langone Medical Center. Do not disclose or use except as authorized in writing by the study sponsor
Interventional Template Version: 11 January 2019

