Laser-assisted 5-FU and laser-assisted TAC have shown similar efficacies in treating hypertrophic scars, though laser-assisted 5-FU has fewer side effects.¹ Laser-assisted topical triamcinolone is associated with the side effects of topical corticosteroids, including sporadic erythema, telangiectasias, hyperpigmentation, hypopigmentation, and a risk of dermal atrophy and fat atrophy.^{8,24}

Building upon previous research, in our study we will investigate the effectiveness of laser-assisted 5-FU and laser-assisted triamcinolone in the treatment of keloids. We will measure "effectiveness" by taking measurements of the height, width, and length of treated lesions prior to, during, and after laser-assisted drug delivery. Analyzing keloids on height, width, and length with calipers allows for 3-dimensional statistical analysis of the effects of the treatments. Similar scar measurement protocols have been used in other studies on pathological scarring.¹

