2.2.1 Clinical Data to Date

In 2013, Waibel *et al.* used ablative fractional photo-thermolysis CO₂ laser treatments to aid corticosteroid delivery in hypertrophic scars. Three to five laser treatments at 2-month to 3-month intervals were combined with a thin topical layer of TAC suspension of 10 or 20 mg/mL, depending on the location and thickness of the skin. They observed an overall scar improvement, with the therapy having the greatest impact on texture but also improved dyschromia and overall appearance.⁸

Park *et al.* compared laser-assisted topical corticosteroid with intralesional corticosteroid injections in keloids. First, the entire keloid was treated with fractional ablative Er:YAG laser. The lesions were subsequently divided into two halves, with the first half receiving intralesional TAC injection (10 mg/mL) and the second receiving topical application of desoxymethasone 0.25% ointment. Four treatments at 6-week

CONFIDENTIAL

This material is the property of the NYU School of Medicine and Langone Medical Center. Do not disclose or use except as authorized in writing by the study sponsor
Interventional Template Version: 11 January 2019

intervals were conducted. They found a statistically significant improvement in the Vancouver Scar Scale (VSS) for both modalities, but the corticosteroid injection was associated with much more severe pain.¹²

In 2019, Waibel *et al.* compared clinical outcomes of hypertrophic scars treated with laser-assisted corticosteroid delivery versus laser-assisted 5-FU delivery. Subjects underwent 3 treatment sessions at 1-month intervals consisting of fractional ablative CO₂ laser treatment followed by postoperative application of either TAC solution (20 mg/mL) or 5-FU solution (50 mg/mL). Scars treated with both modalities demonstrated reduction in overall scar surface area. There was no statistically significant difference between the arms, suggesting that neither agent possesses superior efficacy over the other. However, 5-FU was not associated with the side effect risks that topical corticosteroids foster such as dermal atrophy or telangiectasia formation.¹

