3.2 Secondary Objective

The secondary objective is to assess the differences between both Sites in change in size of keloids post treatment.

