4.2.2 Secondary Study Endpoint

The secondary endpoint is measurements of the scar in both Sites of the keloid. The measurements will be calculated as the total volume (length x width x height) in cm³ of the scar, or length x width in cm² if the scars are flush with the surrounding skin scar surface in the two Sites of the keloid.

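### The scar-size endpoint changes from cm³ to cm² when a site becomes flush, so a fully flattened site has no valid change from baseline and can be recorded as having grown

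*Combined protocol and SAP*

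**What the plan says.** The size measure is defined in three places, each with the same switch of unit.

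- **Protocol Summary, Secondary Study Endpoints:** volume in cm³, or "length x width in cm² if the scars are flush with the surrounding skin". A further sentence reads "Scar surface will be measured in both Sites of the keloid treated with laser-assisted 5-FU delivery as compared to laser-assisted TAC", but it does not make area an endpoint of its own or link it to the switch.
- **Section 4.2.2:** the same definition, with the condition worded "if the scars are flush with the surrounding skin scar surface in the two Sites of the keloid".
- **Section 10.2.4:** volume, or "length x width in cm^2 if the scars are flush with the surrounding skin scar surface".

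The objective in Section 3.2 is to "assess the differences between both Sites in change in size of keloids post treatment", so the quantity of interest is a change. The whole of the planned analysis is: "Measurements of the scar will be summarized by visit and compared between the two Sites of the keloid". No section gives a volume for a flush scar, fixes the unit at baseline, or says how a cm³ value is to be set against a cm² value.

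**The concern.** Keloids are overgrown scars and shrinkage is the intended benefit, so the flush clause will matter mostly after treatment has worked. A site that goes from raised to flush is the best possible response on this objective, and it is the one case the definition cannot handle. Its change from baseline is an area minus a volume, which has no meaning as a quantity. In a within-patient comparison the same problem arises whenever one site is flush and the other is not.

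An analyst who follows the text has two choices. Putting both values in one variable can score complete flattening as growth. Analysing each unit separately drops flattened sites from the volume comparison, which excludes data because of the outcome. Section 2.1 makes caliper size the study's measure of effectiveness and says "Analyzing keloids on height, width, and length with calipers allows for 3-dimensional statistical analysis of the effects of the treatments". That three-dimensional analysis breaks down at the point of greatest response.

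**Working it through.** The plan states no figure for scar size, so there is none to reproduce. Its only calculated figures, in Section 10.1, concern POSAS and are not used here.

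**Inputs.** From the plan: the two formulas, the units, and n = 20. Assumed, because the documents give no dimensions: a 4 × 2 cm footprint (A = 8 cm²), baseline height h of 0.3 to 1.5 cm, and a fraction r of the footprint remaining at Visit 5 of 50% to 100%.

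**One site, raised at Visit 1 and flush at Visit 5, both values in one variable.**

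- Baseline value = A × h (cm³)
- Flush value = r × A (cm²)
- Ratio = r / h, so the recorded number rises whenever h < r

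| h (cm) | Baseline, 8 × h | r = 1: 8.0 | r = 0.7: 5.6 | r = 0.5: 4.0 | True volume change |
|---|---|---|---|---|---|
| 0.3 | 2.4 | +233% | +133% | +67% | −100% |
| 0.5 | 4.0 | +100% | +40% | 0% | −100% |
| 0.8 | 6.4 | +25% | −12.5% | −37.5% | −100% |
| 1.5 | 12.0 | −33% | −53% | −67% | −100% |

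At heights above r the number does fall, but the reduction is understated.

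**The measure is not monotone.** With the footprint unchanged, a site 0.05 cm high scores 8 × 0.05 = 0.4. The same site when flush scores 8.0.

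**The direction depends on the unit of length.** A 40 × 20 × 5 mm site that becomes flush goes from 4000 mm³ to 800 mm², a fall. In centimetres it goes from 4 cm³ to 8 cm², a rise.

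**Comparison between sites.** Both sites are 4 × 2 × 0.5 cm at baseline (4.0 cm³), with r = 0.7 at Visit 5.

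- Flush site, as written: 5.6 − 4.0 = +1.6
- Other site, still 0.1 cm high: 8 × 0.7 × 0.1 = 0.56, and 0.56 − 4.0 = −3.44
- Difference as written: 1.6 − (−3.44) = +5.04, against the flush site
- Difference in true volume: (0 − 4.0) − (−3.44) = −0.56, in favour of the flush site

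The gap between the two answers is 5.04 + 0.56 = 5.6, which is r × A. The distortion therefore does not depend on baseline height.

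A second pair shows that reversal does not need a thin keloid. Both sites start at 4 × 2 × 1.5 cm (12.0 cm³) and keep their footprint; one becomes flush and the other halves in height. As written: (8 − 12) − (6 − 12) = +2.0. In true volume: (0 − 12) − (6 − 12) = −6.0.

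**Effect on a mean of 20 pairs.** Each patient with one flush site of this footprint moves the mean paired difference by r × A / 20: 5.6/20 = 0.28 at r = 0.7, 4.0/20 = 0.20 at r = 0.5, and 8.0/20 = 0.40 at r = 1.

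**The case against.** The strongest reply is that the defect is narrow and the harm hypothetical. Change in cm³ is valid for a site raised at both visits, and change in cm² for a site flush at both; only a site whose flush status changes is affected. Section 10.2.4 labels the units and does not tell anyone to pool them. The Summary's sentence on scar surface can be read as making area available for both sites throughout. Length, width and height are recorded at every visit, so an analyst could recover a sound measure later. The dimensions above are assumed, complete flattening may be rare, and the endpoint is secondary with no power calculation.

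Much of this is right about scope. The problem is confined to sites that change status, or to pairs in different units, and with no SD for size the shift of 0.20 to 0.40 cannot be called large or small.

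The alternative readings do not remove the defect:

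- Fixing the unit by baseline status would work, but no section says so.
- Section 4.2.2's plural wording could mean area is used only when both sites are flush. That avoids mixed units at one visit but not in the change from a raised baseline.
- Reporting the units separately removes the best responders from the volume comparison.
- Leaving the choice until analysis invites a decision made with the results in view.

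**Conclusion.** The concern holds. For a site raised at Visit 1 and flush at Visit 5, the definition as written gives a change that mixes cm² and cm³. This is a stated rule that gives a wrong result, not merely a missing detail. If both values share one variable, full flattening is recorded as growth when baseline height in cm is below the remaining footprint fraction (below 1 cm only if the footprint is unchanged), and the comparison between sites can change sign.

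The sizes shown rest on assumed dimensions, and the number of sites that will become flush is unknown, so the effect on the trial's result cannot be stated. Change in volume remains valid for sites that stay raised. The primary endpoints and the sample size are untouched. The point should be corrected before analysis, but it does not threaten the main conclusions.

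**What to change.** Amend the Protocol Summary, Section 4.2.2 and Section 10.2.4 to say:

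1. A flush site has height 0 and therefore volume 0 cm³.
2. The secondary analysis is the within-patient change in volume (cm³) from Visit 1 to Visit 5, 5-FU site versus TAC site, for every site.
3. Surface area (length × width, cm²) is a separate measure, reported for every site at every visit. This gives effect to the Summary's sentence on scar surface.

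The first item cures the unit problem. The second ties the analysis to the objective in Section 3.2, and the third keeps the information on area that the present definition was trying to preserve.

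The cost is a wording change in three places, with IRB review under Section 12.2. No new data are needed: Sections 7.2.1 and 7.2.2 already require height, length and width at Visits 1 to 5.
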